14.1 Definitions

Adverse event

An adverse event (AE) is any untoward medical occurrence (i.e., any unfavorable and unintended sign, including abnormal laboratory findings, symptom, or disease) in a clinical investigation subject after written informed consent has been provided for participation in the study. Therefore, an AE may or may not be temporally or causally associated with the use of the device.

In the following differentiation between medical history and AEs, the term “condition” may include abnormal physical examination findings, symptoms, diseases, laboratory findings, and electrocardiogram findings.

- Conditions that started before signing of informed consent and for which no symptoms or treatment are present until signing of informed consent are recorded as medical history (e.g., seasonal allergy without acute complaints).

- Conditions that started before signing of informed consent and for which symptoms or treatment are present after signing of informed consent, at *unchanged intensity*, are recorded as medical history (e.g., allergic pollinosis).
- Conditions that started or deteriorated after signing of the ICF will be documented as AEs.

Serious adverse event (SAE)

Any untoward medical occurrence that, at any dose, meets any of the following criteria (a—g):

- a. Results in death.
- b. Is life-threatening.

The term ‘life-threatening’ refers to an event in which the subject was at risk of death at the time of the event, it does not refer to an event which hypothetically might have caused death if it were more severe.

- c. Requires inpatient hospitalization or prolongation of existing hospitalization.

A hospitalization or prolongation of hospitalization will not be regarded as an SAE if at least one of the following exceptions is met:

- The admission results in a hospital stay of less than 12 hours.
- The admission is pre-planned
(i.e., elective, or scheduled surgery arranged prior to the start of the study).
- The admission is not associated with an AE
(e.g., social hospitalization for purposes of respite care).

However, it should be noted that invasive treatment during any hospitalization may fulfill the criterion of ‘medically important’ and as such may be reportable as an SAE dependent on clinical judgment. In addition, where local regulatory authorities specifically require a more stringent definition, the local regulation takes precedence.

- d. Results in persistent or significant disability / incapacity.

Disability means a substantial disruption of a person’s ability to conduct normal life’s functions.

- e. Is a congenital anomaly / birth defect.
- f. Results in fetal distress, fetal death or a congenital abnormality or birth defect.
- g. Is another medically important serious event as judged by the Investigator.

Unanticipated adverse device effect (UADE)

An unanticipated adverse device effect (UADE) is any SAE, or any life-threatening problem or death caused by, or associated with, a device, if that effect, problem, or death was not previously identified in nature, severity, or degree of incidence in the investigational plan or application or any other unanticipated serious problem associated with a device that relates to the rights, safety, or welfare of subjects.

AE Severity and Relatedness

Each AE occurring in the study will be characterized by the study Investigator as to severity and relatedness.

AE Severity Grading System.

Severity Grade	AE Description
Mild	AE is transient and easily tolerated by the subject, even if it causes discomfort
Moderate	AE causes the discomfort and interrupts usual activities
Severe	AE causes considerable interference with usual activities and may be incapacitating or life-threatening

AE Relatedness Grading System. *

Grade	Relationship of AE to study device	Description
5	Definite	An event that follows a reasonable temporal sequence from administration of the study device; that follows a known or expected response pattern to the study device; and that is confirmed by improvement on stopping.
4	Probable	An event that follows a reasonable temporal sequence from administration of the study device; that follows a known or expected response pattern to the study device; and that is unlikely to have been caused by concurrent/underlying illness or other drugs, procedures, or other causes.
3	Possible	An event that follows a reasonable temporal sequence from administration of the study device; that follows a known or expected response pattern to the study device; but may have been caused by concurrent/underlying illness, drugs, procedure, or other causes.
2	Unlikely	An event that does not follow a reasonable temporal sequence from administration of the study device; that does not follow a known or expected response pattern to the study device, or most likely was caused by concurrent/underlying illness, drugs, procedure, or other causes, because of their known effects.
1	Not related	An event almost certainly caused by concurrent/underlying illness, drugs, procedure, or other causes.

*Note that an AE occurring before treatment with the study device will be categorized as unrelated to the study device.

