	subjects may be enrolled in the study in order to meet comparable distribution of samples described in the protocol.
Inclusion and Exclusion Criteria	
Inclusion Criteria:
 
 1. The subject is between 18 and 99 years of age. 2. The subject or Legally Authorized Representative (LAR) is able and willing to provide written informed consent. 3. The subject is planning to undergo a routine skin biopsy. 4. The subject is willing and able to remain still for periods of up to 3 minutes to allow for image capture. 5. The subject or LAR has sufficient mental capacity to understand the informed consent form (ICF) and comply with the protocol requirements. 
Exclusion Criteria:
 
 1. The subject has a general health condition or systemic disease that in the opinion of the physician, precludes them from trial participation. 2. The subject has a known allergy or increased skin sensitivity to silicone, adhesives, or glycerin. 3. The subject's lesion targeted for biopsy: 
 a. Is located on the palms of the hands, soles of the feet, fingernails, or toenails. b. Has dense hair that will not be removed prior to the skin biopsy. c. Has clinically significant abraded or ulcerated skin with or without discharge. d. Is associated with a wound or skin condition that in the opinion of the physician precludes them from participation e. Is located in mucosal tissue (i.e., oral, nasal, etc.). f. Is on tattooed skin. g. Is on a skin formation too tortuous for the investigational device to access (e.g., skin tags.) h. Is located in the periorbital region or directly on the eyelid.
Investigational Device	
VIO, the investigational device, is a noninvasive real-time skin imaging device that can provide histology-like images of skin epithelial tissue with subcellular resolution and dye-free color contrast.
 
The system uses a handheld reflectance confocal and multiphoton microscope that contacts skin [REDACTED] [REDACTED], [REDACTED] [REDACTED], without damaging the tissue. [REDACTED]

Duration of subject participation	Single visit with a 7-day (\pm 3 days) follow-up phone call to assess for adverse events.
-----------------------------------	--

4 Introduction

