6.1.3 Imaging Time

Study Investigator(s) or designee(s) may optionally collect more images for up to 30 total minutes of intermittent imaging.

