10.2 Inclusion Criteria

- The subject is between 18 and 99 years of age.
- The subject or Legally Authorized Representative (LAR) is able and willing to provide written informed consent.
- The subject is planning to undergo a routine skin biopsy.
- The subject is willing and able to remain still for periods of up to 3 minutes to allow for image capture.
- The subject or LAR has sufficient mental capacity to understand the informed consent form (ICF) and comply with the protocol requirements.

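### Relatedness grade 5 (Definite) rests on improvement after stopping, which cannot separate causes for events that start after a single imaging session, and unlike grade 4 it does not require other causes to be unlikely

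*Combined protocol and SAP*

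**What the plan says.** The table in section 14.1 grades each adverse event from 1 to 5 for its relation to the device, and the investigator assigns the grade. Grades 3, 4 and 5 begin with the same two conditions: plausible timing after device use, and a pattern known or expected for the device. Only the third clause differs:

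- Grade 5, Definite: the event is one "that is confirmed by improvement on stopping".
- Grade 4, Probable: "and that is unlikely to have been caused by concurrent/underlying illness or other drugs, procedures, or other causes".
- Grade 3, Possible: "but may have been caused by concurrent/underlying illness, drugs, procedure, or other causes".

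The exposure is short. Under section 3 each subject has one visit and one follow-up call at 7 days, give or take 3. Under section 6.1.3 the operator "may optionally collect more images for up to 30 total minutes of intermittent imaging". Under section 12.6 the imaged skin is the planned biopsy site plus an uninvolved site, preferably contralateral.

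Section 8.2 makes adverse event incidence a primary endpoint and breaks it down by relatedness, among other factors.

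**The concern.** Improvement after withdrawal is useful evidence when exposure continues and can be interrupted. Here use ends within one visit, so for an event that appears that evening or two days later there is nothing left to stop. The clause also stands where grade 4 has its exclusion of other causes. The top grade is therefore not stricter than the grade below it on the question that matters most in this design: whether the device or the biopsy at the same site caused the event.

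Two to five sites will apply the table, and the text does not say which reading they should use. With at most 65 subjects, one or two reclassified events could visibly change the relatedness rows of the safety table.

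**Working it through.** The documents give no figure to reproduce, and no sample size, error rate or event count depends on this wording. The check sets the definitions against the design.

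**Step 1: what separates the grades (section 14.1).**

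| Grade | Timing and expected pattern | Other causes | Improvement on stopping |
|---|---|---|---|
| 5 Definite | required | not addressed | required |
| 4 Probable | required | must be unlikely | not addressed |
| 3 Possible | required | may be present | not addressed |

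Grade 5 does not contain grade 4's condition, so an event can satisfy 5 without satisfying 4. Nothing in grade 5 contradicts grade 3, so one event can satisfy both.

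**Step 2: which events the third clause can inform.** Section 14.4 lists the expected device risks: adhesive irritation, allergic reaction to fluid or cover, pain from wand pressure or a sensitive lesion, and infection. Pain, irritation and infection could also follow a biopsy. That the biopsy comes after imaging is inferred from the word planned in section 12.6; no sentence states the order.

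**Step 3: three example records, graded as written.**

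| Event | Strict reading (improvement must follow stopping) | Loose reading (any later improvement counts) |
|---|---|---|
| A. Wand-pressure pain during imaging, eases when the wand is lifted | 5 available | 5 available |
| B. Sticker dermatitis at a contralateral uninvolved site, day 2 to day 5 | 5 closed; at most 4 | 5 available |
| C. Irritation at the biopsied lesion, starts after the biopsy, gone by day 4 | 5 closed; 3 fits | 5 and 3 both fit |

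Record A shows the clause working: section 12.1 schedules an adverse event assessment on the imaging day, so the improvement can be seen. Record B has no planned biopsy as a rival cause, yet the strict reading bars it from Definite. Record C has an obvious rival cause, yet the loose reading admits it to Definite.

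**Step 4: size of the shift.** Between readings, record B moves from 4 to 5, one grade (5 − 4 = 1). Record C moves from 3 to 5, two grades (5 − 3 = 2).

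**Step 5: does the word procedure already cover the biopsy?** Grades 3 and 4 list procedures among other causes. Section 12.1, however, labels VIO imaging itself as the study procedure, so the word does not point clearly to the biopsy. Grade 5 does not mention other causes at all.

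**The case against.** The best defence is that the strict reading is the ordinary one. An event that began after the device was removed is not confirmed by its removal, so record C goes to grade 3 and the overlap disappears. The investigator judges each event, and section 14.6 has a medical monitor reviewing adverse event reports. The endpoint is descriptive, with no threshold or test, and the visible reporting text in section 14.2.2 does not depend on grade 4 versus 5. Section 7 says no adverse events had been observed, although the context is partly redacted, so the number of affected records may be zero.

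Much of this stands, and it limits the importance of the point. It does not repair the rule. The strict reading closes the top grade to every event that starts after imaging, however clear its cause. No visible text selects that reading or gives the medical monitor the task of regrading.

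A reader might also infer that grade 5 can never be met, or that any transient event meets it. The documents support neither. Pain or irritation that starts during the session can ease when contact ends and be recorded the same day. An event unlike an expected device response fails the second condition on either reading. Nor does the shortness of imaging relative to the follow-up week measure how many events are misgraded: that would need onset spread evenly over the week, which nothing in the documents supports, and the contact time of sticker and fluid is not given.

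**Conclusion.** The point holds as a minor defect in a stated rule. For events that start after imaging, the grade 5 criterion is either inapplicable or uninformative. Because grade 5 lacks grade 4's exclusion of other causes, Definite is not reliably stricter than Probable and can overlap with Possible.

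The effect is a shift of one or two grades for an affected record, confined to the relatedness breakdown of the primary safety endpoint. How many records are affected cannot be estimated from the documents. Total adverse event incidence, sample size and both effectiveness endpoints are untouched.

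The conclusion assumes that imaging precedes the biopsy and that sticker, cover and fluid are removed by the end of the session. If the sticker stayed on longer, the period in which improvement is informative would lengthen somewhat, but the missing exclusion of other causes would remain.

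**What to change.** Change the grade 5 row of the section 14.1 table:

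1. Keep the two conditions it shares with grades 3 and 4.
2. Replace the third with grade 4's exclusion in a stricter form: no other cause is plausible, with the biopsy named explicitly among the causes to be considered.
3. State that improvement on ending device contact is supporting evidence for events that began during imaging, and is not required for events that began later.

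Grades 3, 4 and 5 then run in order: other causes possible, unlikely, not plausible. Any CRF instructions that repeat the scale should be aligned.

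Grade 5 should not be limited to events confined to contacted skin. That would bar a spreading allergic reaction, which section 14.4 anticipates, and it could not be examined in a phone call.

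The cost is a short text change, with no added subjects or visits. Some events may move between grades 3, 4 and 5. In particular, most skin events at the biopsied lesion that start after the biopsy will not reach Definite. That reflects what the design can show, since it cannot separate the two causes at that site.

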14.2 Reporting of Adverse Events

14.2.1 Assessments and documentation of adverse events

The Investigator or designee must collect all AEs for each subject from the time of the start of device procedure preparation to 7 days (\pm 3 days) following the end of subject study participation, whether or not deemed related to the investigational device or procedure. All AE data will be recorded on the CRF. All AEs will be followed until the event has subsided or, for a minimum of 30-days after subjects' participation has ended.

14.2.2 Reporting of serious adverse events

These include device deficiencies (DDs) that may have led to a SAE if a) suitable action had not been taken or b) intervention had not been made or c) if circumstances had been less fortunate. These are handled under the SAE reporting system.

- Notification of the IRB: Notification of the IRB about all relevant events (e.g., SAEs, UADEs, device malfunctions) will be performed by the Investigator according to all applicable requirements.
- Notification of the authorities: The processing and reporting of all relevant events (e.g., SAEs, UADEs, device failures, device malfunctions) to the authorities will be done by the Sponsor according to all applicable regulations.

14.3 Risks and Benefits

14.3.1 Benefits

There is no direct health benefit to the participant. The primary benefit of this study comes from the scientific knowledge gained about the capabilities of reflectance confocal and multiphoton microscopy to display clinically relevant features of cellular structure and skin architecture noninvasively.

14.3.2 Risks

The risks of this study and use of the device to image skin are considered to be no more than minimal. The VIO procedure described in this protocol is very similar to RCM imaging of skin with commercially available devices.

- **Skin:** The VIO device takes an image of skin tissue by exciting and reflecting light off the tissue with laser light, which could introduce the risk of tissue damage if the light power was above a safety threshold. The VIO, however, uses an ultrafast pulsed laser to maintain an overall low average power level²⁶ so tissue is not damaged, while still providing the high instantaneous intensities needed for reflectance confocal and multiphoton microscopy.
- **Eyes:** Light from the probe tip diverges rapidly, which decreases light power density as a function of distance from the probe tip (Class 1M laser). As such, eye protection for the user is not be required.

²⁷

The VIO procedure is also similar to commonly performed office-based dermoscopy procedures. Similar to dermoscopy, the VIO procedure involves non-invasive illumination of skin and magnification of skin structures. A systematic review found that, among the 433 abstracts that addressed dermoscopy, “no study systematically assessed harms to either patients or the operators from the use of dermascope.”

Two case reports described possible harm due to dermoscopy: (1) dermoscopy immersion oil contaminated with cedarwood oil was reported to have caused allergic contact dermatitis in one patient, and (2) intensive use of dermoscopy may have caused tonic pupil (Adie’s pupil) in a dermatologist.²⁸ Concerns have also been raised about patient risk for nosocomial infection when contact dermoscopy is used and the dermascope is not fully cleaned between patients.²⁸

14.4 Potential Risks to Study Subjects

The following are the possible risks associated with the VIO procedure:

- Irritation from adhesive targeting guide
- Allergic reaction such as irritation or sensitivity to immersion fluid or cover
- Pain due to pressure from the wand and/or sensitivity of the lesion
- Infection caused due to improper cleaning of the device

14.5 Risk Mitigation

VIO will limit the risk of allergic contact dermatitis by using an immersion fluid approved to be used in medical settings (e.g., pharmaceutical grade glycerin). Additionally, the VIO device comprises materials generally considered biocompatible when used in similar devices for similar applications (e.g., silicone). The users will be trained thoroughly on device use to mitigate the risk of patient experiencing any pain during the sessions.²⁸ We will mitigate the risk of infection in this protocol by using a single use imaging cover and cleaning it with an alcohol swab prior to use.

14.6 Medical Monitoring

A medical monitor will be appointed for the study. The medical monitor will be a physician who is not involved in conducting the study and who has no conflict of interest. The medical monitor is responsible for ongoing monitoring of adverse event reports to identify safety concerns quickly.

15 Data Handling and Record Keeping

15.1 Confidentiality

All records identifying the subject will be kept confidential and, to the extent permitted by the applicable laws and/or regulations, will not be made publicly available.

Subject names will not be supplied to any people or organizations outside of the Sponsor and Investigators. Only the subject code will be recorded in the CRF. Study findings stored on a computer will be stored in accordance with local data protection laws. As part of the informed consent process, the subjects and/or LARs will be informed in writing that representatives of the Sponsor, IRB, or regulatory authorities may inspect their medical records to verify the

information collected, and that all personal information made available for inspection will be handled in strictest confidence and in accordance with local data protection laws. The data may also be used for future research, development and commercial activities and any identifying information will be kept confidential and described in the consent form. If the results of the study are published, the subjects' identities will remain confidential. The Investigator will maintain a list to enable subjects to be identified.

the first time in the history of the world, the people of the United States have been called upon to determine whether they will submit to the law of force, or the law of the Constitution. We have said to the world, we will not submit.

11. **What is the primary purpose of the *Journal of Clinical Endocrinology and Metabolism*?**

11. **What is the primary purpose of the following statement?**

11. **What is the primary purpose of the *Journal of Clinical Endocrinology and Metabolism*?**

11. **What is the primary purpose of the *Journal of Clinical Endocrinology and Metabolism*?**

16 Device Malfunction

16.1 Definitions

Device malfunction

A device malfunction is a failure of the device to meet its performance specifications or otherwise perform as intended when used in accordance with the IFU (User Manual).

Device misuse

A device misuse occurs when the Investigator or designee uses the device in a manner that is contradictory to the IFU (User Manual). A device misuse will not be considered a malfunction.

16.2 Recording and Addressing Device Malfunction

Throughout the study, the Investigator and study staff will report and document all device malfunctions related to the identity, quality, durability, reliability, safety, or performance of the device.

17 Study Monitoring, Auditing, and Inspecting

Representatives of the Sponsor will visit all study sites to perform monitoring and data management functions, and provide participating sites with relevant contact information, as necessary.

18 Ethical and Legal Considerations

18.1 Compliance with Good Clinical Research Practice

This study will be conducted in compliance with the principles of the Declaration of Helsinki, with the current Good Clinical Practice (GCP) guidelines and with other applicable regulations. The Investigator and all study staff will conduct the study in compliance with this protocol. Voluntary informed consent will be given by every subject or LAR prior to the initiation of any study-related procedures. The rights, safety and well-being of the study subjects are the most important considerations and prevail over the interests of science and society. All personnel involved in the conduct of this study must be qualified by education, training and experience to perform their assigned responsibilities.

